Statistical analysis strategy: Descriptive statistics of endothelial dysfunction measures (FMD%, NTMD%), soluble VCAM, soluble ICAM, sFLT-1, VEGF, heme oxygenase activity and rho/rho kinase activity will be presented by treatment and by visit, along with corresponding charts. FMD% and NTMD% will be log-transformed. To evaluate the effect of atorvastatin on endothelial dysfunction measures, we will perform a comparison of treatment by visit, using Student t-test subsequently followed by crossover ANOVA model testing carry-over effect and treatment effect. For soluble VCAM, soluble ICAM, sFLT-1, VEGF, heme oxygenase activity and rho/rho kinase activity, since they are not normally distributed, we will compare atorvastatin with placebo using Wilcoxon sign rank test. Similar analysis will be performed for the albuminuria and estimated GFR values. In addition, the relationship between outcome measures and treatment will be studied through a multiple regression analysis.

To evaluate the effect of atorvastatin on albuminuria, we will examine albuminuria both as a continuous variable using a linear mixed model to analyze the effect and as a categorical variable using a generalized estimating equation approach. Point estimates and confidence interval for the effect of albuminuria will be presented. Distribution of any complication among patients by treatment will be presented. The association of side effects by treatment will be tested using McNemar's test.

Differences in pre- and post- treatment echocardiographically-defined TRV will be described in tabular and graphical terms. (Added 06/04/2013.)

Sample Size Justification: Based on previous literature (70), we assume a standard deviation of 0.894 for changes in mean FMD%. In a 2x2 crossover design, the minimum required sample size is 9 per sequence to detect a clinically meaningful difference of 0.65 in mean changes in FMD% between atorvastatin and placebo groups at significance level $\alpha = 0.05$ with 80% power. Assuming a 5% attrition rate, we will enroll 19 patients for this study. (Revised 06/03/2013.)

Anticipated Outcomes: We anticipate that atorvastatin, by improving endothelial dysfunction, will decrease albuminuria in SCD. Furthermore, atorvastin will increase HO activity, but decrease rho kinase activity, sFLT-1 levels and TF-mediated sFLT-1 release from monocytes.

Potential Pitfalls: The main limitation in this exploratory study is that 6 weeks of treatment with atorvastatin may not be adequate to achieve an improvement in endothelial dysfunction assessed by flow mediated

vasodilation or improvement in the estimated GFR. If the results suggest a promising risk-benefit ratio for the effects of atorvastatin on endothelial function, parameter estimates from the clinical intervention will be used to determine the most appropriate design and sample size requirements for a more definitive study.

As hydroxyurea may affect endothelial function and is associated with decreased plasma levels of endothelial markers in SCD patients, the benefits of atorvastatin may be less for patients on hydroxyurea. To deal with these issues, patients on hydroxyurea will be on a stable dose for at least 3 months prior to starting the study and the dose will only be changed for safety reasons. In addition, analyses of the results will be adjusted for treatment with hydroxyurea as a post stratification variable.

Feasibility: The UNC Comprehensive Sickle Cell Program is well suited to conduct the studies proposed here. Our program consists of a dedicated group of clinical researchers, nurses and scientists who have a track record of high quality clinical and laboratory-based studies. We have extensive experience in the conduct of clinical studies as proposed here. We will use the services of the NC TraCs Institute and the CTRC at UNC, Chapel Hill, with such resources as a state of the art database system, an investigational drug pharmacy, research ultrasound laboratory, and outpatient facilities where study patients will be evaluated. The UNC Comprehensive Sickle Cell Program provides care to ~ 350 adults and 350 children with SCD. In addition to a weekly sickle cell clinic, we have a weekly clinical and research meeting where patient cases and research studies are discussed. This practice model fosters efficient accrual of subjects onto clinical research studies.

Data Management: For all study aims, a standardized set of data collection forms will be designed using the RED Cap system and a secure database will be created to support the compilation of study-specific information. All data will be stored under password protection on a secured server. A data manager will handle all data entry and the security of the database. This individual will work closely with the statistician on database design and quality assurance procedures.

Timeline: The projected study duration is 5 years. We anticipate beginning recruitment within 3-6 months of the start date. This time period is required to confirm the presence of albuminuria. Recruitment is expected to take up to 48 months. The remaining few months will be dedicated to completing the studies, data analysis and publication.

HUMAN SUBJECTS

This human subjects' research meets the definition of a clinical trial. An Investigation New Drug (IND) application to the FDA to support the administration of atorvastatin to SCD patients is pending. (***FDA determined the study to be EXEMPT from IND. Letter on file.***)

Protection of Human Subjects

1. Human Subjects Involvement and Characteristics: This study seeks to evaluate the contribution of endothelial dysfunction to the pathophysiology of albuminuria in SCD. It involves the conduct of a study to evaluate the effect of atorvastatin on endothelial dysfunction and albuminuria in SCD. Nineteen patients with SCD (HbSS or S β ⁰ thalassemia) that meet the eligibility criteria will be enrolled in a randomized, double-blind, placebo-controlled, crossover trial. At the time of enrollment, all study subjects will be in the non-crisis, steady state. Informed consent will be obtained according to IRB approved procedure. Patients will be closely monitored for adverse events following randomization to the study drug. The primary goal of this study is to evaluate the effect of atorvastatin on endothelial dysfunction (FMD and NTMD). Furthermore, we will evaluate plasma markers of endothelial activation (soluble VCAM, soluble ICAM), plasma levels of sFLT-1, VEGF, nitric oxide metabolites, heme oxygenase activity, rho/rho kinase activity, tissue factor-mediated sFLT-1 release from monocytes, albuminuria, estimated glomerular filtration rate and safety as described in the application.

2. Sources of Research Material: Enrollment and study participation will involve the collection of a full range of clinical data, including medical history. We will obtain brachial artery ultrasound data, as well as clinical and laboratory data at specified intervals during the course of the studies as described in the research plan.

3. Plans for Recruitment: Patients will be recruited from amongst the patients that routinely receive their care at the UNC Comprehensive Sickle Cell Program. [name] and/or one of his co-investigators will discuss the studies with all eligible patients. Interested patients will be provided with a copy of the consent form(s), and the study coordinator or PI (or a co-investigator) will carefully go over the consent with each candidate before he/she signs. We will strive to ensure that all patients understand the nature of the study and all their questions will be answered. The original consent form will be placed in the study files, in a secure, locked cabinet. Potential subjects will be contacted during regularly scheduled clinic visits, but may be contacted at home by study personnel if they are known to meet the eligibility criteria. The PI and study nurse involved in the study are regular staff of the program. Samples obtained from patients specifically for these studies will be collected as approved by the IRB. This is anticipated to occur during specified study visits.

4. Potential Risks: The clinical study with ancillary studies entail minor physical risk associated with venipuncture to obtain blood samples; administration of atorvastatin; administration of nitroglycerin; and pneumatic occlusion cuff placed around the upper forearm to a suprasystolic pressure (~ 200 mmHg) during the assessment of flow-mediated vasodilation. The most significant risks of blood tests are discomfort and bruising. There is extensive clinical experience with the use of atorvastatin, although there are no published studies using this drug in SCD. Atorvastatin is well tolerated in the general population. However, as the most common complications of statins are liver function test (LFT) abnormalities and myopathy, we will exclude those patients with significant liver disease or history of a myopathy. In addition, as SCD patients have low cholesterol levels, lipid profiles will be monitored closely. Nitroglycerin commonly causes a headache, and less often hypotension, dizziness and lightheadedness. We will exclude patients with systolic blood pressure < 90 mmHg, severe aortic stenosis, and hypertrophic obstructive cardiomyopathy. Headaches associated with nitroglycerin use are typically short lasting and respond to acetaminophen. Pneumatic occlusion of the forearm to a suprasystolic pressure is uncomfortable. However, this technique has been safely performed in SCD patients. Patients will be monitored very closely for any laboratory or clinical complications during the course of the studies.

5. Procedures for Minimizing Risks: We will do everything possible to minimize the risks associated with participating in the studies. For patients receiving nitroglycerin during assessment of flow-mediated vasodilation, we will ensure there are no contraindications to receiving this drug. In addition, we will obtain baseline laboratory studies (including liver function tests and creatine kinase) prior to commencement on the study and monitor them closely during the course of the study due to the small risk of worsening LFT and myopathy with atorvastatin. This study will be monitored by a DSMB, which will review all reports to determine if there is a safety concern. Finally, we have established data safety and monitoring procedures as described below.

Risks to Privacy: All clinical information, including personal identifiers obtained on research subjects will be maintained in a locked and secured file drawer with access limited to clinical staff. All data will be coded to protect patient confidentiality. We will make all effort to maintain patient confidentiality.

6. Potential Benefits of the Proposed Research to the Subjects and others: The projects proposed in this application will help to define the contribution of endothelial dysfunction to the pathogenesis of albuminuria in SCD. The available treatments of nephropathy in SCD remain limited. Treatment with atorvastatin may provide clinical benefit.

7. Importance of the Knowledge to be Gained: Despite our improving understanding of the pathophysiology of SCD, treatment options for several SCD-related complications remain quite limited. This proposal aims to increase our understanding of the pathogenesis of albuminuria in SCD and evaluate the efficacy and safety of

atorvastatin in SCD-associated nephropathy. The risks to patients from participating in this study are modest and are reasonable in relation to the potential benefits and the importance of knowledge to be gained.

8. Data and Safety Monitoring Plan: All SAEs will be reported to the IRB and the DSMB. The DSMB will review these data quarterly and notify the Principal Investigator if safety appears to be an issue in the study. In addition, after 5 patients and then 10 patients are enrolled, all of the available safety data will be presented by treatment group to the DSMB in a confidential report. The DSMB will review and determine if there is a safety concern. The study will be terminated at the occurrence of treatment-related serious adverse events, including transaminitis or myopathy, in up to three study participants.

The UNC TraCS DSMB is a committee that has been established within the UNC School of Medicine. The membership is appointed by the Dean (or his designee), and is available to review any clinical trial that is being carried out by a UNC investigator. Most multi-center clinical trials funded by the NIH or by industry have national data and safety monitoring boards organized by the sponsoring organization. However, single- or dual-site clinical trials such as the study proposed in this application depend on a local DSMB such as the one based here at UNC. The current makeup includes a chair ([name]), an ethicist, an epidemiologist/biostatistician, and several clinical researchers. In addition, *ad hoc* members are added to the DSMB when need for scientific expertise arises.

9. Inclusion of Women and Minorities: Based on the results of our studies in this patient population to date, we anticipate that enrolled subjects will include 50-55% women. We have achieved this in the past without special efforts to recruit women, and this reflects the gender distribution of our patient population. In addition, due to the nature of the disease to be studied (sickle cell disease), over 95% of patients will identify themselves as African-American. A small number identifying themselves as Hispanic or Native American may be available; such patients typically comprise less than 2% of our clinic patients with this disease.

10. Inclusion of Children: As the prevalence of albuminuria in children is thought to be lower than in adults, we anticipate that most of our study patients will be adults.

REFERENCES

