Clinical and Laboratory Evaluations: The Screening/Baseline Phase will occur within 28 days of study drug administration and will include: informed consent, a history and physical examination, and clinical laboratory tests including: a complete blood count, routine coagulation studies, routine chemistries to assess liver and renal function, lipid profile, creatine kinase, urine microalbumin-creatinine ratio, chest x-ray, and serum pregnancy test (if female, and of child-bearing capacity). During the first visit of each Treatment Phase, prior to treatment initiation, we will also obtain a complete blood count, routine chemistries to assess liver and renal function, lipid profile, creatine kinase, urine microalbumin-creatinine ratio, serum pregnancy test (if female). Finally, measurements of endothelial dysfunction (assessed non-invasively using a brachial artery shear stress method), endothelial activation (soluble

Title of the Protocol: The effect of atorvastatin on endothelial dysfunction and albuminuria in sickle cell disease

VCAM, soluble ICAM), sFLT-1, VEGF, heme oxygenase activity, rho/rho kinase activity, tissue factor (TF) expression, TF-mediated sFLT-1 release from monocytes, estimated GFR and microalbumin-creatinine ratio will be obtained at specified time points during the Baseline, Treatment and Washout/Follow-up Phases. The Follow-up Phase will consist of safety assessments performed four weeks after the final dose of study treatment.

Sample Size: In a 2x2 crossover design, the minimum required sample size is 9 per sequence to detect a clinically meaningful difference of 0.65 in mean changes in FMD% between atorvastatin and placebo groups at significance level $\alpha = 0.05$ with 80% power. Assuming a 5% attrition rate, we will enroll 19 patients in the study.

Randomization: 1:1 randomization to receive atorvastatin or placebo.

BACKGROUND, SIGNIFICANCE AND RATIONALE

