
An Investigational New Drug (IND) application to support the administration of atorvastatin to SCD patients is pending. (**FDA determined study to be EXEMPT from IND. Letter on file.**)

Inclusion Criteria:

- a) HbSS or HbS β^0 thalassemia between ages of 18 and 70; (**Maximum age revised 06/03/2013 and 04/07/2015.**)
- b) albuminuria (micro- or macroalbuminuria, defined as ≥ 30 mg/g creatinine);
- c) serum ALT ≤ 2 times upper limits of normal and/or GGT (**added 05/12/2015, revised 06/13/2017**) ≤ 3 times upper limits of normal;
- d) platelet count $\geq 150,000$ cu/mm;
- e) normal baseline coagulation profile (PT/INR, PTT);
- f) non-crisis, steady state with no severe pain episodes during the preceding 4 weeks, and no documented infection in the 2 weeks prior to enrollment; (**infection added 8/26/11**)
- g) ability to understand the requirements of the study;
- h) if a woman of childbearing potential, must use an adequate method of contraception; and
- i) if receiving hydroxyurea, ACE inhibitors or ARBs, should be on a stable dose for at least 3 months.

Exclusion Criteria:

- a) hypersensitivity to any component of atorvastatin, **or history of adverse reaction to statins;** (**ADDED 8/26/2011**)
- b) pregnant or breastfeeding;
- c) on statin therapy;
- d) history of metastatic cancer;
- e) current history of alcohol abuse;
- f) history of diabetes mellitus or poorly controlled systemic hypertension;
- g) end-stage renal disease;
- h) total cholesterol level < 80 mg/dL and LDL cholesterol > 130 mg/dL;
- i) on a chronic transfusion program;
- j) ingested any investigational drugs within the past 4 weeks;
- k) prior history of any myopathy;
- l) allergy to nitroglycerin;
- m) *taking any of the following drugs: phosphodiesterase-5 inhibitors (e.g., sildenafil), CYP3A4 inhibitors (e.g., cyclosporine, protease inhibitors), macrolide antibiotics (e.g., clarithromycin, erythromycin), fibric acid derivatives (e.g. gemfibrozil), niacin, colchicines, antifungal agents (azole derivatives), amiodarone, danazol, daptomycin, diltiazem, verapamil, eltrombopag, everolimus, fosphenytoin, or lanthanum.*

Patients will also be encouraged to avoid grape fruit juice and red yeast rice for the duration of the study.

Atorvastatin is contraindicated during pregnancy and breast-feeding. (Added 08/26/2011.)

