Termination Criteria: Treatment with study drug will be discontinued at any time if the patient: a) withdraws consent; b) develops ALT > 3 times upper limits of normal or GGT (**added 05/12/2015, modified 6/13/2017**) > 5 times upper limits of normal; c) develops symptoms and signs consistent with myopathy (muscle weakness and increased levels of creatine kinase); or if, d) in the judgment of the investigator, continuation of the study drug will be hazardous to the patient. The study will be terminated at the occurrence of treatment-related serious adverse events, including transaminitis or myopathy as above, in up to 3 study participants.

Treatment: Subjects will receive atorvastatin 40 mg/day or placebo for 6 weeks and after a 4-week wash-out period will be “crossed-over” to receive 6 weeks of whichever treatment they did not receive initially. Pill counting will be used to assess compliance. If toxicity occurs the study drug will be discontinued and the patient followed until resolution of the problem. Subjects discontinued prematurely will continue to follow-up for efficacy assessments.

Assessments:

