Endothelial Activation, sFLT-1, VEGF, heme oxygenase activity, rho/rho kinase activity and TF-mediated sFLT-1 release: We will measure plasma levels of soluble VCAM and soluble ICAM, plasma levels of sFLT-1 and VEGF (ELISA kits from R&D systems) and assess heme oxygenase and rho/rho kinase activities (see below) at baseline and then at week 6 of both treatment periods. Flow cytometry will be performed to assess monocyte activation state, absolute cell counts, TF expression, as well as TF-mediated sFLT-1 release from monocytes at baseline and at week 6.

Heme oxygenase activity: Heme oxygenase-1 (HO-1) protein in plasma will be determined (ELISA kit from Cusabio Biotech, Newark, DE) according to the manufacturer's directions. Tandem experiments will be performed using human microvascular endothelial cells (Lonza, Allendale, NY) to determine the ability of blood from SCD patients to induce HO-1 expression (94) and activity (95). **Rho/rho Kinase Activity:** The

activity of rho kinase will be assayed by western blotting with a phospho-specific and activation specific antibody (Anaspec) as previously described (96), in lysates prepared from the endothelial cells exposed to blood.

Renal Function – We will assess the effect of atorvastatin on albuminuria by spot urine microalbumin/creatinine ratio and estimated GFR at baseline, Week 4 and Week 6 of both treatment periods.

Safety – Subjects will be evaluated for safety throughout the study by history-taking, measurement of vital signs, physical examinations, and routine laboratory tests (CBCs, and chemistries including liver function tests, creatine kinase, lipid profile, and tests of renal function). In addition to abnormal liver function tests, myopathy, and other adverse events, we will monitor subjects for SCD-related events (Appendix 1).

Doppler echocardiography will be performed at baseline and at Week 6 in each study arm to examine the relationship of endothelial dysfunction, assessed using ultrasound imaging of the brachial artery, with tricuspid regurgitation velocity (TRV). (Added 06/04/2013.)

A hemoglobin analysis will be performed at screening to confirm diagnosis of sickle cell anemia (or HbS- β^0 thalassemia). (Added 08/26/2011.)

Statistical Methods: (revised 08/26/2011; revised 05/31/2013.)

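### Exclusion criterion h) joins two lipid limits that no patient can meet together, so read literally it excludes nobody

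*Combined protocol and SAP*

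**What the plan says.** Under Exclusion Criteria, item h) reads "total cholesterol level < 80 mg/dL and LDL cholesterol > 130 mg/dL". It is the only place in the protocol where a cholesterol value decides eligibility.

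Lipids are measured before entry. The screening laboratory list under Clinical and Laboratory Evaluations includes "routine chemistries to assess liver and renal function, lipid profile, creatine kinase, urine microalbumin-creatinine ratio, chest x-ray", and the schedule of assessments marks a lipid profile at screening. Human Subjects, item 4 (Potential Risks), adds that "as SCD patients have low cholesterol levels, lipid profiles will be monitored closely".

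For the liver tests, Inclusion Criteria item c) requires "serum ALT ≤ 2 times upper limits of normal and/or GGT" at no more than 3 times the upper limit of normal (ULN). Termination Criteria item b) stops study drug when a patient "develops ALT > 3 times upper limits of normal or GGT" above 5 times ULN. Potential Risks also says that "we will exclude those patients with significant liver disease or history of a myopathy", without giving a laboratory threshold.

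**The concern.** An exclusion with two conditions joined by *and* acts only on patients who meet both. In h) one condition asks for very low total cholesterol and the other for high LDL, which pull in opposite directions. If no patient can meet both, the rule does nothing. The protocol would then have no working lower limit on cholesterol in a population that it describes as having low cholesterol, before a lipid-lowering drug is given. It would have no working upper limit on LDL either.

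The liver criterion raises a lesser question of the same kind. *And/or* can mean that both limits must be satisfied or that one is enough, and the two readings can give opposite decisions on the same pair of results.

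**Working it through.** No sample-size or power figure enters this point. The check is one of logic.

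**Exclusion h).** Inputs: the two thresholds in h), 80 and 130 mg/dL. Assumption: both values come from the same lipid profile, so LDL ≤ total cholesterol (TC), because LDL is one of its parts.

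- If TC < 80, then in whole mg/dL LDL is at most 79, which is not above 130.
- If LDL > 130, then TC is at least 131, which is not below 80.
- To meet both, LDL would have to exceed TC by more than 130 − 80 = 50 mg/dL, which is impossible.

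Counting all whole-number pairs with TC from 30 to 400 and LDL from 0 to TC:

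- All pairs: the sum of (TC + 1) is (31 + 401) × 371 / 2 = 80,136.
- TC < 80: (31 + 80) × 50 / 2 = 2,775.
- LDL > 130: 270 × 271 / 2 = 36,585.
- Both: 0.
- Either: 2,775 + 36,585 = 39,360.

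So the rule is empty with *and* and can act with *or*. These counts show only whether the sets are empty. They are not patient frequencies.

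The rest of the exclusion list is informative about wording. Items a), b) and f) each name two alternative reasons for exclusion and join them with *or*. Item h) departs from that pattern, and no other section restates it.

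**Inclusion c), side note.** Inputs: entry limits of 2 × ULN (ALT) and 3 × ULN (GGT); stopping levels of > 3 × ULN (ALT) or > 5 × ULN (GGT).

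| ALT (× ULN) | GGT (× ULN) | Both must hold | Either is enough | Above a stopping level? |
|---|---|---|---|---|
| 2 | 3 | eligible | eligible | no |
| 3.5 | 3 | not eligible | eligible | yes, ALT |
| 2 | 5.5 | not eligible | eligible | yes, GGT |

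Take a grid from 0 to 8 × ULN in steps of 0.25, which has 33 values per test. Nine ALT values are ≤ 2, and thirteen GGT values are ≤ 3.

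- *Both*: 9 × 13 = 117 eligible points, none above a stopping level.
- *Either*: 9 × 33 + 13 × 33 − 117 = 609 eligible points. Of these, 20 × 13 = 260 have ALT > 3 and 9 × 12 = 108 have GGT > 5, so 368 lie above a stopping level.

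Again, this shows only that the sets overlap under one reading and not under the other.

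**The case against.** The best reply on h) is that the joint reading is so plainly impossible that nobody would apply it. A clinician would take the line as a list: exclude total cholesterol below 80, and exclude LDL above 130. That is probably what was meant, and both thresholds are stated. It is a good argument about intent, but it does not correct the rule. The neighbouring criteria use *or* for alternatives, and the literal text excludes nobody.

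A second reply is that the stated safeguard is monitoring of lipids, which runs whatever h) says. The Safety paragraph does list "chemistries including liver function tests, creatine kinase, lipid profile, and tests of renal function" among the tests during the study, and a data and safety monitoring board reviews safety. That stands as mitigation. Monitoring after entry is still not an entry limit. It is also fair to say that the documents give no reason for the LDL limit and do not state that total cholesterol below 80 is hazardous on atorvastatin.

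On c), the objection largely succeeds. The GGT limits in c) and in Termination Criteria b) carry the same amendment dates (05/12/2015 and 06/13/2017), so they look like a matched pair: 2 and 3 times ULN to enter, 3 and 5 times ULN to stop. The stated exclusion of significant liver disease points the same way. The investigator may also stop drug if "in the judgment of the investigator, continuation of the study drug will be hazardous to the patient". Recruitment is from a single program, so inconsistent application is less likely. What remains is that the words allow both readings and none of these safeguards supplies an entry threshold.

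A reader might go further and infer that GGT is not measured because the laboratory lists do not name it. Those lists do not name ALT either, so nothing follows from the omission.

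**Conclusion.** Exclusion h) is wrong as written. Under the sole assumption that LDL cannot exceed total cholesterol in the same profile, no patient can meet it, and neither of its thresholds acts. Two separate exclusions were probably intended, but only the sponsor can confirm that.

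The liver wording in c) is a side note. The overlap with the stopping levels exists only under the *either* reading, which is the less likely one. Even with *and*, the gaps of 3 − 2 = 1 × ULN for ALT and 5 − 3 = 2 × ULN for GGT hold at screening only. Screening may be up to 28 days before dosing, and no stated rule reapplies c) at the start of either treatment period.

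Two stronger conclusions are tempting and not supported. One is that patients were wrongly admitted or put at risk: nothing in the documents shows this, and without distributions of cholesterol, ALT or GGT the number of the 19 patients affected cannot be estimated. The other is that the trial's statistics are compromised: sample size, power and the FMD analysis do not depend on either criterion.

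**What to change.** In exclusion h), replace *and* with *or*, or split it into two items: total cholesterol < 80 mg/dL; LDL cholesterol > 130 mg/dL. The sponsor should confirm that this was the intent.

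In the same amendment, replace *and/or* in inclusion c) with *and*, so that the ALT limit (2 × ULN) and the GGT limit (3 × ULN) both bind at screening, again with the sponsor's confirmation. This would also give the stated exclusion of significant liver disease a laboratory threshold.

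The cost is a short wording amendment and possibly a few more screen failures. Lipids and liver chemistries are already drawn at screening, so no visit is added.
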